4 STUDY POPULATION

4.1 Subject population

A minimum of 200 subjects will be enrolled in the study following satisfactory completion of a screening visit where eligibility for the study will be checked. Males and females will be included from the age of 65 and over. At least a hundred subjects will be above the age of 70. Subjects will be randomised to participate in the morning or afternoon to have an equal time of day distribution.

Subjects will be recruited via media advertisement or from the subjects' database of the Centre for Human Drug Research, Leiden, the Netherlands.

4.2 Inclusion criteria

- 1. Males and females, aged 65 and older (inclusive);
- 2. Willing and able to perform the cognitive tests, as evidenced by performance on the training session of the cognitive tests;
- 3. Willing and able to give written informed consent.

4.3 Exclusion criteria

- 1. Legal incapacity or inability to understand or comply with the requirements of the study;
- Evidence of cognitive deterioration, as indicated by a diagnosis of a cognitive disorder (including but not limited to MCI, Alzheimer's disease, Lewy Body Dementia, Frontotemporal Dementia);
- 3. History or symptoms of significant psychiatric disease in the past 3 years (including but not limited to clinical depression, schizophrenia);
- 4. A Mini Mental State Examination (MMSE) score of ≤24;
- 5. A Geriatric Depression Scale 15 (GDS) score of ≥6;
- 6. Presence of drug abuse, or positive urine drug screen (UDS) at screening or occasion;
- Presence of severe alcohol abuse (daily alcohol consumption exceeding 2 standard drinks per day on average for females or exceeding 3 standard drinks per day on average for males (1 standard drink = 10 grams of alcohol)), or a positive breath alcohol test at screening or occasion;
- 8. Any contradictions for a lumbar puncture as judged by the principal investigator;
- 9. Any other reason that it is not safe or ethical to allow a subject to participate in the study in the opinion of the investigator.

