VVLT recognition	X ²					X					
Milner Maze Test (MMT) immediate	X ²			X							
MMT reversed	X ²			X							
MMT delayed	X ²				X						
Face encoding and recognition test	X ²				X						
N-Back	X ²						Х				
Sustained Attention to Response Test	X ²				X						
Finger tapping	X ²							X			
Electroencephalography (EEG)					X						
Smooth & saccadic eye movements	X ²			Х							
Clinical Dementia Rating scale			Χ								
Instrumental Activities of Daily Living scale			X								

¹ At the end of the study day, the first 20 subjects will rate the burden of the study by answering a Visual Analogue Scale question. These 20 subjects will also be contacted by telephone 48 hours after LP to check for AEs.

² PD tests training session.

JAMAR dynamometry						Χ			
Plasma sample biomarker research			X^3			X		X ⁴	
Blood sample genotyping			Χ						
CSF sampling							X		
Discharge	Х							X	
Con-meds		<>							

_

³ Subjects will be unfed for first plasma biomarker sample due to the influence of fat on the adequate isolation of exosomes from plasma. Subjects will be offered breakfast/lunch thereafter.

⁴ Plasma sample closest to CSF sample (4h sample) will be used to compare CSF and plasma biomarkers.

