2 STUDY OBJECTIVES

Main objectives:

To define an algorithm based on the plasma biomarkers: A β 40, A β 42, t-Tau, p-Tau, NfL and APOE ϵ status and NeuroCart tests, age, grip strength and level of education that distinguishes between positive and negative A β CSF in healthy elderly.

Exploratory objective:

To determine the correlation between AD-specific biomarkers in CSF (Aβ 1-40 and 1-42, Tau proteins, NfL) and the NeuroCart scores in a cohort of 200 healthy elderly subjects.

To determine the correlation between AD-specific biomarkers in plasma (Aβ 1-40 and 1-42, Tau proteins, NfL) the NeuroCart scores in a cohort of 200 healthy elderly subjects.

To determine the correlation between AD-specific biomarkers in CSF (Aβ 1-40 and 1-42, Tau proteins, NfL) and in plasma in a cohort of 200 healthy elderly subjects.

To determine the correlation between APOE ϵ genotype and the A β /Tau/NfL concentrations in CSF in a cohort of 200 healthy elderly subjects.

To determine the correlation between APOE ϵ genotype and the A β /Tau/NfL concentrations in plasma in a cohort of 200 healthy elderly subjects.

To characterize the cohort of healthy elderly subjects in order to yield norm scores for specific NeuroCart tests in all subjects.

To characterize the plasma biomarkers across multiple times of day to gain understanding of intraand inter-subject variability, and thus diurnal fluctuation.

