4.4 Study population subgroups

General cognitive functioning, dementia status and depressive status will be assessed at pre-study screening. All subjects eligible according to the in- and exclusion criteria will be entered in the study. Subjects will be asked to give consent for a LP.

Plasma levels of A β 40, A β 42 and NfL, APOE ϵ status and NeuroCart tests of the 200 subjects will be used to define an algorithm that will be able to improve the efficiency of finding healthy subjects who have an A β positive (CSF) profile. The subjects will be divided in a group yielding subjects who are suspected of AD pathology (ADpath+) by the algorithm and subjects who are suspected to be without AD pathology (ADpath-)

To confirm the correct classification potential of the algorithm, the outcome will be compared to the CSF Aβ outcome of the subjects. CSF ADpath+ and a CSF ADpath- defined by an Aβ 1-42 CSF

level ≤450 pg/mL for ADpath+ subjects and an Aβ 1-42 CSF level ≥451 pg/mL for ADpath- subjects, will be used to differentiate between the two groups.

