4.5 Referral to specialized memory clinic

Before participation in this study, subjects will be tested for eligibility. To check if a subject is able to give consent, the subjects will be screened on cognitive and psychiatric functioning at screening. The general practitioner of each subject will be informed about possible study participation, following written consent from the subject.

When a previously presumed cognitively healthy elderly subject is showing signs of dementia, as defined by a MMSE score of ≤18, or when a subject fulfills the criteria of prodromal AD (MCI and a positive CSF biomarker profile (Aβ 1-42 level ≤450 ng/L)), a referral to the specialized memory clinic of the Vrije Universiteit University Medical Center (VUmc) will be discussed. The diagnosis of MCI is met according to the following criteria: (1) memory complaints, (2) normal activities of daily living, (3) normal general cognitive function, (4) abnormal memory for age, and (5) not demented [28]. At the memory clinic of the VUmc, further diagnostics (e.g. MRI) and counselling will take place.

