The same system as used for saccadic eye movements is also used for measurement of smooth pursuit. For smooth pursuit eye movements, the target moves at a frequency ranging from 0.3 to 1.1 Hz, by steps of 0.1 Hz. The amplitude of target displacement corresponds to 22.5 degrees eyeball rotation to both sides. Four cycles are recorded for each stimulus frequency. The time in which the eyes are in smooth pursuit of the target will be calculated for each frequency and expressed as a percentage of stimulus duration. The average percentage of smooth pursuit for all stimulus frequencies will be used as parameter.

CDR

The Washington University Clinical Dementia Rating (CDR) is used in longitudinal studies and clinical trials for staging the severity of Alzheimer's disease (AD). The CDR is derived from a semi structured interview with the patient and rates impairment in each of six cognitive categories (Memory, Orientation, Judgment and Problem Solving, Community Affairs, Home and Hobbies, and Personal Care) on a five-point scale in which none = 0, questionable = 0 5, mild = 1, moderate 2, and severe = 3. (Note Personal Care has no questionable impairment level) From the six individual category ratings, or "box scores," the global CDR is established by clinical scoring rules which CDR 0 = no dementia and CDR 0.5, 1, 2 or 3 indicates questionable, mild, moderate or severe dementia [53].

IADL

The instrumental activities of daily living scale was developed to asses complex activities necessary for functioning in community settings (e.g. shopping, cooking, managing finances). The capacity to handle these complex functions normally is lost before basic 'activities of daily living' (e.g. eating, bathing, toileting) which are measured by ADL scales. Therefore assessing IADL may identify incipient decline in older adults or otherwise capable and healthy. The IADL contains 8 items that are rated with a summary score and takes around 10 minutes [54].

JAMAR dynamometry - handgrip strength

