9.5 Analysis sets

Data of all subjects participating in the study will be included in the analyses if the data can meaningfully contribute to the objectives of the study.

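### Undiagnosed MCI or CDR 0.5 with an MMSE of 25 or more can enter the healthy-elderly cohort, and no stated rule uses the study-day CDR when the norm scores and the algorithm are derived

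*Protocol*

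**What the plan says.** **Entry.** Protocol section 4.3 excludes "Evidence of cognitive deterioration, as indicated by a diagnosis of a cognitive disorder", with MCI among its examples. A separate criterion excludes "A Mini Mental State Examination (MMSE) score of ≤24". Section 4.2 also requires that the subject can do the cognitive tests, judged at the training session. Section 4.4 states: "General cognitive functioning, dementia status and depressive status will be assessed at pre-study screening". Section 3.1.1 names the MMSE and the GDS-15 as the instruments for this.

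**CDR.** In Table 1 the row "Clinical Dementia Rating scale" has no mark under screening and one mark at 0h on study day 1. Section 7.3 explains the scale: "CDR 0 = no dementia and CDR 0.5, 1, 2 or 3 indicates questionable, mild, moderate or severe dementia".

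**MCI found later.** Section 4.5 provides for discussing a referral "when a subject fulfills the criteria of prodromal AD (MCI and a positive CSF biomarker profile". Its definition of MCI combines normal general cognition with memory that is abnormal for age.

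**Analysis.** Section 9.5 says "Data of all subjects participating in the study will be included in the analyses", on condition that the data can contribute meaningfully to the objectives. Section 2 aims the algorithm at healthy elderly and asks for "norm scores for specific NeuroCart tests in all subjects". The predictors named in that main objective are plasma markers, APOE, NeuroCart tests, age, grip strength and education. Section 9.8.1 describes the LASSO candidates more broadly, as the CNS and the biochemical outcomes plus age and education. Section 6.2 lists CDR sum of boxes among the CNS outcomes.

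**The concern.** The algorithm and the norm scores are both described as results for healthy elderly. The entry criteria do not fully secure that description, and the one dementia staging scale in the trial is collected without any stated use in defining who counts as healthy.

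Two results are exposed. First, section 7.3 reports from earlier studies that NeuroCart performance is lower in elderly people with below-normal cognition and lowest in AD. If impaired participants are also more often Aβ positive, some of the discrimination credited to the NeuroCart would come from recognising impairment, not from finding pathology in healthy people. A CDR predictor would do this directly. Second, norm scores that include impaired subjects are too low, so later subjects with a real deficit would more easily look normal.

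**Working it through.** **1. Can an impaired subject enter?** Take an undiagnosed subject with abnormal memory for age and an MMSE of 25 or more.
- Diagnosis criterion (4.3): not triggered, because there is no diagnosis.
- MMSE criterion (4.3): not triggered. By section 4.5, MCI is compatible with normal general cognition, so this criterion does not rule MCI out.
- Training session (4.2): tests whether the subject can do the tests. No cut-off is given.
- CDR: taken after eligibility has been decided, and named in no criterion.

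Such a subject can therefore enter. CDR 1 is restricted by the MMSE cut-off but not ruled out.

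**2. Is the subject handled afterwards?** Section 4.5 needs a CSF result, so it applies after the lumbar puncture. It gives a referral and says nothing about the data. Section 9.5 has no cognitive rule. Section 2 takes norms from all subjects.

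**3. The plan's own figure.** Section 1.1.4 expects 100 × 0.23 + 100 × 0.19 = 23 + 19 = 42 Aβ-positive healthy subjects. This reproduces and is not disputed.

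**4. Possible size.** None of these inputs is in the documents, except that 19% is the protocol's own rate for ages 65 and over. Assume an impaired share f of 5, 10 or 15%; a NeuroCart score with SD 1 in both groups, oriented so that lower is worse, and 1.5 SD lower in impaired subjects; Aβ positivity of 45% in impaired subjects and 19% in the rest; and no relation between score and Aβ status within either group.

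Impaired share among positives: p₊ = 0.45f / [0.45f + 0.19(1−f)]. Among negatives: p₋ = 0.55f / [0.55f + 0.81(1−f)].

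c-index = 0.5 + (p₊ − p₋) × [Φ(1.5/√2) − 0.5], with Φ(1.061) = 0.856.

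The 5th-percentile norm q solves fΦ(q + 1.5) + (1−f)Φ(q) = 0.05.

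| f | p₊ | p₋ | c-index | q (SD) | Healthy below q | Impaired below q |
|---|---|---|---|---|---|---|
| 0 | – | – | 0.500 | -1.64 | 5% | 44% |
| 5% | 0.0225/0.203 = 11.1% | 0.0275/0.797 = 3.5% | 0.527 | -1.84 | 3.3% | 37% |
| 10% | 0.045/0.216 = 20.8% | 0.055/0.784 = 7.0% | 0.549 | -2.02 | 2.2% | 30% |
| 15% | 0.0675/0.229 = 29.5% | 0.0825/0.771 = 10.7% | 0.567 | -2.18 | 1.5% | 25% |

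With equal positivity in both groups, p₊ = p₋ and the c-index stays at 0.5. The shift in the norm does not depend on positivity at all.

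**5. Size of a global CDR = 0 set.** Aβ positives remaining: 190 × 0.19 = 36.1, 180 × 0.19 = 34.2, 170 × 0.19 = 32.3. The number set aside is 200f × 0.45 = 4.5, 9 or 13.5.

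**The case against.** The strongest reply is that the protocol has a workable definition of healthy (no diagnosis, MMSE above 24, GDS-15 below 6), that the study is declared exploratory, and that a CDR of 0 is merely a stricter definition. It would also cost Aβ positives in a study that already expects few events per variable. This stands against making CDR = 0 an entry criterion or the primary set for the algorithm. It does not answer the norm scores, or the lack of any check on what drives discrimination.

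Several stronger readings are tempting, and the documents do not support them:
- *Only people with an existing diagnosis are rejected.* The MMSE cut-off and the training session also remove undiagnosed subjects.
- *Section 4.4 contradicts Table 1 because the CDR is not at screening.* Section 4.4 does not name the CDR. Section 3.1.1 assigns dementia screening to the MMSE, which Table 1 does place at screening.
- *Subjects with dementia will enter every analysis.* The text shows only that some impaired subjects can enter, and section 9.5 carries a condition, though a vague one.
- *The CDR is definitely an intended predictor.* The wording in section 9.8.1 is loose. Read literally it would also admit the CSF markers, including the one that defines the outcome.

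The analysis plan is not at hand and may define the sets further. It cannot change who enters, and the protocol itself fixes norm scores in all subjects.

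**Conclusion.** The point holds as a gap, not as a wrong figure. Undiagnosed MCI, or CDR 0.5, with an MMSE of 25 or more can enter a cohort reported as healthy elderly. The study-day CDR would identify subjects rated 0.5 or higher, but nothing in the protocol says what follows for the norm scores or the algorithm. The candidate list in section 9.8.1 is also wider than the main objective.

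The size cannot be derived from the documents. Under the assumptions shown, the spurious c-index is modest (0.53-0.57). The norm effect matters more: the 5th-percentile limit falls to between -1.84 and -2.18 SD, and the share of impaired subjects below it drops from 44% to 25-37%. A reader should not conclude that such contamination will occur at this level. The conclusion is that the protocol cannot detect or exclude it in its reported results, although the data to do so are collected.

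**What to change.** 1. In section 9.5, define a cognitively healthy set: global CDR = 0, from the study-day CDR.
2. Derive the NeuroCart norm scores from that set, and amend the norm-score objective in section 2, which now says all subjects.
3. Keep the all-subject analysis of the algorithm, and pre-specify a repeat of its calibration, discrimination and prediction-error assessment in the global CDR = 0 set as a sensitivity analysis.
4. Align the candidate list in section 9.8.1, and its copies in the synopsis and section 1.1.9, with the main objective, so that CDR sum of boxes is not a predictor.
5. Reconcile sections 4.3 and 4.5 on subjects found to have MCI after entry, and state how their data are used.

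The cost is a few sentences and no new procedure. The norm set becomes smaller, 170-190 instead of 200 under the assumed 5-15%. The sensitivity set has about 32-36 Aβ positives against the planned 42, so its estimates will be less precise and should be read beside the all-subject result, not in place of it.

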4.4 Study population subgroups

General cognitive functioning, dementia status and depressive status will be assessed at pre-study screening. All subjects eligible according to the in- and exclusion criteria will be entered in the study. Subjects will be asked to give consent for a LP.

Plasma levels of A β 40, A β 42 and NfL, APOE ϵ status and NeuroCart tests of the 200 subjects will be used to define an algorithm that will be able to improve the efficiency of finding healthy subjects who have an A β positive (CSF) profile. The subjects will be divided in a group yielding subjects who are suspected of AD pathology (ADpath+) by the algorithm and subjects who are suspected to be without AD pathology (ADpath-)

To confirm the correct classification potential of the algorithm, the outcome will be compared to the CSF Aβ outcome of the subjects. CSF ADpath+ and a CSF ADpath- defined by an Aβ 1-42 CSF

level ≤450 pg/mL for ADpath+ subjects and an Aβ 1-42 CSF level ≥451 pg/mL for ADpath- subjects, will be used to differentiate between the two groups.

4.5 Referral to specialized memory clinic

Before participation in this study, subjects will be tested for eligibility. To check if a subject is able to give consent, the subjects will be screened on cognitive and psychiatric functioning at screening. The general practitioner of each subject will be informed about possible study participation, following written consent from the subject.

When a previously presumed cognitively healthy elderly subject is showing signs of dementia, as defined by a MMSE score of ≤18, or when a subject fulfills the criteria of prodromal AD (MCI and a positive CSF biomarker profile (Aβ 1-42 level ≤450 ng/L)), a referral to the specialized memory clinic of the Vrije Universiteit University Medical Center (VUmc) will be discussed. The diagnosis of MCI is met according to the following criteria: (1) memory complaints, (2) normal activities of daily living, (3) normal general cognitive function, (4) abnormal memory for age, and (5) not demented [28]. At the memory clinic of the VUmc, further diagnostics (e.g. MRI) and counselling will take place.

4.6 Concomitant medications

Any medication which affects the central nervous system is not allowed as judged by the principal investigator. All prescription and over-the-counter (OTC) medications, vitamins, herbal and dietary supplements used at screening and occasion will be recorded.

4.7 Lifestyle restrictions

Approximate meal times will be according to the study schedule. Poppy seed or foods containing poppy seeds are not permitted from 3 days before screening.

Alcohol will not be allowed from at least 24 hours before screening and before the study day. Between screening and the study visit, daily alcohol consumption exceeding 2 standard drinks per day on average for females or exceeding 3 standard drinks per day on average for males will not be permitted (one unit is 10 grams of alcohol). Subjects will undergo an alcohol breath test the morning of the study day.

Subjects will not be allowed to have excessive caffeine consumption, defined as >800 mg per day from 7 days prior to the study day. Subjects will abstain from caffeine-containing products for 24 hours prior to the start of the screening and study day. Caffeine quantities defined as: one cup of coffee contains 100 mg of caffeine; one cup of tea, or one glass of cola, or potion of chocolate (dark:100 g, milk 200 g) contains approximately 40 mg of caffeine; one bottle of Red Bull contains approximately 80 mg of caffeine.

Strenuous physical activity (e.g., heavy lifting, weight or fitness training) is not allowed from 48 hours prior to the screening. Light ambulatory activities (e.g. walking at normal pace) will be permitted.

Subjects are asked not to use NSAIDs (e.g. ibuprofen, diclofenac) in the ten days prior to the study day till one day after the study day (LP).

Subjects will be required to fast 4 hours before the start of the study occasion. Water is allowed as required. Subject will only have to fast for the first blood sample on the study day and will be offered breakfast/lunch thereafter.

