9.8 CNS and biochemical endpoints

9.8.1 NeuroCart

All parameters will be listed by subject.

Parameters will initially be analysed without transformation, but if the data suggest otherwise, log-transformation may be applied.

Descriptive statistics will be used to summarize the data. Data will be graphically processed for visual inspection.

In order to develop an algorithm that can classify the subjects between ADpath+ and ADpath- there will be a two-step procedure. In the first step 500 bootstrap samples will be generated out of the original data and logistic regression with LASSO penalization (in order to account for the expected small event per variable ratio) in each of the bootstrap samples with all the candidate variables (CNS and biochemical outcome variables, age and educational level) will be performed. Out of all the candidate variables the ones that consistently and most frequently appear in the bootstrap models will be selected. Hence, in this first step the variable selection will take place. In the second step another 500 bootstrap samples will be generated and logistic regression will be performed (with penalization if necessary) in each of the bootstrap samples. This time only the variables that were selected in step 1 will be entered in the model. The estimates out of all the bootstrap models will be averaged and used in order to obtain predictions in the original data. Step two will result in the bootstrap-corrected predictions that will be assessed in terms of calibration (calibration slope), discrimination (c-index) and squared mean prediction error.

To investigate the relationship between biomarkers and gene carriers and NeuroCart scores, correlations and regression analyses will be used.

NeuroCart scores will be analysed with an analysis of variance (ANOVA) and/or multivariate analysis of variance (MANCOVA) to estimate differences between the groups of elderly with different Aβ status.

The intra- and inter-individual diurnal fluctuation will be investigated with mixed-model analysis.

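### In both sessions the first plasma sample is fasted and later ones follow a meal, so the change from 0 h cannot by itself be read as diurnal fluctuation

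*Protocol*

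**What the plan says.** Section 2 lists as an exploratory objective: "To characterize the plasma biomarkers across multiple times of day to gain understanding of intraand inter-subject variability, and thus diurnal fluctuation". Section 9.8.1 gives the method in one sentence: "The intra- and inter-individual diurnal fluctuation will be investigated with mixed-model analysis". It names no model terms.

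The sampling conditions are fixed elsewhere in the protocol:

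- Each subject makes one visit of about 4 hours (section 3.1.2), with three biomarker samples (section 7.5), the last at 4 h (Table 1, footnote 4).
- Section 4.7: "Subjects will be required to fast 4 hours before the start of the study occasion", followed by "Subject will only have to fast for the first blood sample on the study day and will be offered breakfast/lunch thereafter".
- Table 1, footnote 3, gives the reason: "Subjects will be unfed for first plasma biomarker sample due to the influence of fat on the adequate isolation of exosomes from plasma".
- Section 4.1: "Subjects will be randomised to participate in the morning or afternoon to have an equal time of day distribution".
- Section 7.2 has the actual clock time of each blood draw recorded.

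The background in section 1 says that what is learned about fluctuation can help to choose times for lumbar punctures and blood samples in later trials.

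**The concern.** The objective moves straight from variability across the visit's samples to diurnal fluctuation. On this schedule, time of day is not the only thing that changes between the first sample and the later ones. Every subject, in either session, also goes from fasted to fed and spends longer on site. Any effect of the meal on a plasma marker would therefore look like an effect of the hour. The result is meant to inform sampling times in future trials, where a meal effect and a clock effect would call for different precautions.

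The design does contain a means of separating the two. Session is randomised and clock time is recorded. The protocol does not connect either to the diurnal question.

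**Working it through.** The protocol states no figure for the diurnal analysis, so there is none to reproduce.

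**Inputs from the protocol:** 200 subjects, taken as about 100 per session; three plasma samples; first at 0 h fasted; last at 4 h after a meal.

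**Assumed:** middle sample at m = 1.5 to 3 h, because the column cannot be read reliably in the available text of Table 1; the offered meal is eaten. The fasted sample is taken to precede the meal, as section 4.7 and footnote 3 say, although Table 1 lists the meal row above the plasma row and section 7.4 asks for top-down order where possible.

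**1. What changes between samples**

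| Step | Clock time | Fasted to fed | Time since meal | Time on site |
|---|---|---|---|---|
| Sample 1 to 2 | yes | yes | starts | yes |
| Sample 2 to 3 | yes | no | yes | yes |

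This is the same in both sessions.

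**2. Sample number as a category.** Two occasion contrasts plus a fed indicator give rank 2 of 3 within subject. Fed state is exactly aliased with occasion. Adding session only as a main effect, with occasion and fed both in the model, gives rank 4 of 5, so the aliasing remains.

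**3. Linear trend plus a fed step.** With t = (0, m, 4) and fed = (0, 1, 1), centred within subject:

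- S_tf = (m + 4)/3
- S_tt = m² + 16 − (m + 4)²/3
- S_ff = 2/3
- r² = S_tf²/(S_tt × S_ff)
- variance inflation of the trend = 1/(1 − r²)
- if fed state is omitted, a meal step of 1 unit with no diurnal effect gives slope b = S_tf/S_tt, so an apparent 4-hour change of 4b

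At m = 2: S_tf = 2, S_tt = 20 − 12 = 8, r² = 4/(8 × 2/3) = 0.75, inflation = 4.0, 4b = 4 × 2/8 = 1.00.

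| m (h) | r | Variance inflation | Apparent 4 h change per unit of meal step |
|---|---|---|---|
| 1.5 | 0.79 | 2.6 | 0.90 |
| 2 | 0.87 | 4.0 | 1.00 |
| 2.5 | 0.93 | 7.3 | 1.06 |
| 3 | 0.97 | 17 | 1.08 |

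The trend is estimable (rank 2 of 2), but it rests on samples 2 and 3 alone.

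**4. Illustration of false positives.** Assume a between-subject SD of 25%, a within-subject SD of 6%, m = 2, no diurnal effect and a model with a clock slope but no fed term. Using within-subject information only, the SE of the slope is 6/√(200 × 8) = 0.15% per hour. A 2% meal shift gives a slope of 2 × 0.25 = 0.50, z = 0.50/0.15 = 3.33, and a two-sided 5% rejection rate of about Φ(3.33 − 1.96) = 0.915. Simulation with assumed starts at 08:00 and 13:00 gave about 90%, and 81% to 96% over m = 1.5 to 3. A 1% shift gave 36% to 43%, and a 5% shift 100%.

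**5. What the randomised session offers**

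- Session contrast on the mean of the two post-meal samples, same SDs: SE = √(25² + 6²/2) × √(2/100) = 25.36 × 0.1414 = 3.6%. Detectable with 80% power: 2.8 × 3.6% ≈ 10%. In simulation its false-positive rate stayed at 2.5% to 7%.
- Clock time (linear, quadratic or 24-hour cosinor) plus a fed indicator over both sessions is full rank for assumed starts of 8/12, 8/13 and 9/13 h. The SE of the fed effect is 0.08 to 0.09 SD at within-subject correlation 0.5, and about 0.05 SD at 0.9.

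**The case against.** The strongest reply is that the protocol commits only to a mixed model. It does not rule out session, clock time or fed state, and it collects what such a model needs. Model terms are commonly left to an SAP, and the SAP is not among the documents. That stands: the unlisted terms are not an error in themselves, and a reader should not infer that the analysis will ignore session. What remains is the reading in section 2, which the schedule does not support whatever the SAP says.

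A reader might also infer that clock time and meal are wholly inseparable. They are not. Samples 2 and 3 are both post-meal, and two sessions with recorded clock times allow the effects to be separated under a stated model. Exact aliasing arises only when occasion is categorical.

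The false-positive rates in step 4 should not be read as a forecast. They need a model that the protocol does not specify and a meal effect for which it gives no figure. The only influence of food it names is that of fat on exosome isolation, and the fasted first sample addresses that.

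Finally, one might extend the point to the other analyses. The documents do not support this. The CSF comparison uses the 4 h sample, which is post-meal in everyone, and session is randomised, so leaving it out does not bias comparisons by Aβ status. No gain is shown from offering session to the algorithm, which already has many candidates for about 42 expected positive subjects.

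**Conclusion.** The concern holds for the interpretation of within-subject change. The change from 0 h to a later sample combines clock time, meal and time on site, and cannot alone support a diurnal conclusion. The change from sample 2 to sample 3 avoids the fasted-to-fed step but not time since the meal.

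Size: if fed state is omitted from a linear time model, essentially the whole meal step (0.90 to 1.08 of it) passes into the apparent 4-hour change. If it is included as a step, the within-subject trend loses precision by a variance factor of 2.6 to 17. Both ranges depend on the assumed middle sample time. How large the error would be in practice depends on the meal effect, which the protocol does not give.

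The consequence is limited to an exploratory objective with no formal hypothesis (section 9.8.2). The main algorithm objective is not directly affected.

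**What to change.** Change wording and analysis only; visits and meals stay as they are.

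1. In section 2, remove the direct step from within-visit variability to diurnal fluctuation. Report the 0 h-to-later change as meal plus elapsed time.
2. In the protocol or SAP, base the diurnal conclusion on a mixed model with a random subject effect that uses the randomised session, in one of two forms:
   - sampling occasion, session and their interaction, with the session contrast read at the post-meal samples; or
   - recorded clock time plus a fed indicator, fitted across both sessions, with the assumed shape of the clock effect stated.
3. State the limits. The session contrast is between subjects. It compares breakfast with lunch. Length of fast at 0 h may differ by session, since morning subjects may have fasted overnight. The second form also assumes that the meal acts as a constant step.

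The cost is precision. Under the assumed SDs, the session contrast has an SE of 3.6%, against 4 × 0.15% = 0.6% for a 4-hour within-subject change from a slope model without a fed term. That smaller SE, however, belongs to a quantity that includes the meal.
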